4.4 Replacement

Subjects will be replaced under the following conditions:

• Subjects who did not receive study medication or did not proceed to surgery or did not undergo lymphatic mapping with lymph node biopsy.

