Table 9 describes the procedures that should be followed based on the in vivo and ex vivo status of the tissue that has been excised.

Table 9.	Handling of Excise	d Tissue
----------	--------------------	----------

In Vivo Assessment	Ex Vivo Assessment	Procedure		
Radioactive Status	Radioactive Status			
positive (hot)	positive (hot)	Send to pathology for further evaluation.		
positive (hot)	negative (not hot) or no counts obtained	Incorrect node harvested. Send to pathology for further evaluation. Return to resection bed.		
negative or no counts (not hot)	positive (hot)	Comment on why lymph node was removed. Send to pathology for further evaluation.		
Vital Blue Dye Status				
Blue node	N/A	ANY blue node is sent to pathology for further evaluation regardless of radioactive status.		

- 8. A thorough evaluation of the remaining lymphatic basin should be undertaken since more than one LN may be found. This evaluation should include a combination of palpation, visualization, and gamma detector survey for evidence of blue and/or increased gamma detector count rates.
- 9. Probing of the area will be complete when all selected node counts are negative by use of the threshold criterion. The surgeon will continue with visualization and palpation according to local practice to ensure that no grossly positive LNs remain at the site of resection.

If a subject has neither a blue node nor any "hot" nodes, continue with visualization and palpation according to your medical expertise.

All removed LNs must be sent to pathology for further evaluation. The pathological evaluation of lymph node(s) will include serial sectioning and staining as described below (see also the Pathology Manual for additional details). For the purposes of analysis, a sentinel lymph node is defined as either being hot in vivo (lymph nodes with counts above the 3σ rule threshold) or blue (when applicable).

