9.8 Handling of Missing Data

There will be no missing value imputation used in this study. All endpoints will be analyzed with subjects who have non-missing data (i.e., a complete case analysis).

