9.9 Statistical Analysis

9.9.1 Analysis Populations

The following analysis populations will be defined:

Safety: The safety population will include all enrolled subjects with administration of Lymphoseek.

Intent-to-treat (ITT): The ITT population will include all protocol-eligible subjects with administration of Lymphoseek (with or without Lymphazurin) and complete intraoperative lymphatic mapping.

Blue intent-to-treat (BITT): The BITT population will include all ITT subjects who were also administered Lymphazurin prior to ILM.

Per protocol (PP): The PP population will include all ITT subjects without major protocol violations.

All safety analyses will be conducted on the safety population. The analysis of the diagnostic endpoints will be conducted on ITT, BITT, and PP populations, as applicable.

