9.9.5 Analysis of Primary Diagnostic Variables

The localization rate, defined as the proportion of ITT subjects that had at least one lymph node identified intraoperatively, along with a 95% confidence interval will be computed for Lymphoseek for each tumor type and overall.

The average number of lymph nodes identified intraoperatively by Lymphoseek per subject, along with a 95% confidence interval, will be computed for each tumor type and overall.

The proportion of ITT subjects who had preoperative SPECT performed will be summarized by tumor type and overall. The proportion of patients who had a hot spot on the scan will also be summarized by tumor type and overall. For those patients with a hot spot, the time from Lymphoseek injection to hot spot localization will be summarized.

The average number of lymph nodes identified with preoperative SPECT per subject, along with a 95% confidence interval, will be computed for Lymphoseek by tumor type and overall.

The average difference in the number of lymph nodes identified with preoperative SPECT per subject and the number of lymph nodes identified intraoperatively per subject, along with a 95% confidence interval, will also be computed.

The nodal and subject agreement of central pathology assessment to local pathology assessment will be computed as follows:

	Lymph nodes whose local and central pathology assessments were either	
Nodal	both positive or both negative	
Agreement =	Lymph nodes with non-missing local and central pathology results	

Where agreement on the subject level means that a subject either has at least one pathologypositive node with local and central pathology or has all pathology-negative nodes with local and central pathology. For the analysis of nodal agreement and subject agreement, only nodes that have non-missing local and central pathology results will be considered. Along with the agreement proportions, a 95% confidence interval will be computed for each endpoint. Subgroup analyses by tumor type will also be performed within the ITT and PP analysis populations.

The nodal false negative rate will be computed for Lymphoseek as the number of pathologypositive lymph nodes that were missed intraoperatively by the tracer divided by the total number of pathology-positive lymph nodes. A 95% confidence interval will also be computed. False negative rates also will be calculated separately for the blinded central pathology assessment and the local pathology assessment.

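### The ITT set behind the localization rate requires complete mapping, an undefined post-injection condition that can leave out subjects whose mapping failed

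*Combined protocol and SAP*

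**What the plan says.** Section 9.9.1 defines the set: "The ITT population will include all protocol-eligible subjects with administration of Lymphoseek (with or without Lymphazurin) and complete intraoperative lymphatic mapping". The synopsis has the same mapping condition but starts from all enrolled subjects instead of eligible ones. BITT and PP are both subsets of ITT.

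Section 9.9.5 gives the localization rate, listed first among the primary diagnostic variables in Section 9.6.1, as "defined as the proportion of ITT subjects that had at least one lymph node identified intraoperatively". A 95% interval is planned by tumor type and overall, with no method named.

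Section 4.4 replaces subjects who received no study medication, or who "did not proceed to surgery or did not undergo lymphatic mapping with lymph node biopsy".

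Section 8.4.2 foresees a failed search. The passage opening "If a subject has neither a blue node nor any" hot node tells the surgeon to go on by sight and touch. It does not say how the subject is classified if no node is then removed. Step 9 of the same section says: "Probing of the area will be complete when all selected node counts are negative by use of the threshold criterion". Nothing links that sentence to ITT membership.

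Section 9.8 plans complete-case analysis without imputation. The safety set keeps every enrolled subject who was injected, but it is not used for localization.

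**The concern.** A localization rate should count the subjects in whom the agent failed to show a node. Here the denominator depends on something that happens after injection and is closely tied to the outcome. Mapping that finds no signal is the mapping most likely to be cut short or judged incomplete. The study is open label, so that judgement is made with the result in view.

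A subject lost this way is always a non-localized one, so the error can run in one direction only. The replacement rule then brings in a further subject, and the final count looks intact. PP cannot correct this, because it is drawn from ITT. At stake is the estimate and interval for a primary diagnostic variable in a study of about 27 subjects, with tumor-type minimums of 6.

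**Working it through.** **Step 1. Trace each kind of subject through the rules.** All are injected and have no hot or blue node.

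| Subject | ITT (9.9.1) | Replaced (4.4) | Effect on localization rate |
|---|---|---|---|
| Node removed by sight or touch | In | No | Counted as non-localized |
| Fully probed, no node removed | Most naturally in; not stated | Yes, on the literal text | Counted as non-localized if in ITT |
| Mapping begun, abandoned for lack of signal, no node removed | Out, on the literal text | Yes | Not counted |
| Mapping never started because imaging showed no drainage | Out | Yes | Not counted |

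The third and fourth rows leave the denominator. The second depends on a reading that the plan does not settle.

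**Step 2. Inputs.** The planned size is approximately 27 (Section 9.7), which agrees with 6 + 6 + 15 = 27. The plan states no expected localization rate, precision target or failure count, so there is no planned figure to reproduce. The number dropped, k, is an assumption (0 to 4). All other subjects are assumed to localize.

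**Step 3. Rate and interval.** The plan would report 27/27; counting the dropped subjects gives 27/(27 + k). I used exact (Clopper-Pearson) limits: lower = Beta quantile at 0.025 with parameters x and n − x + 1; upper = Beta quantile at 0.975 with parameters x + 1 and n − x. When x = n the lower limit is 0.025^(1/n), so for 27/27 it is 0.025^(1/27) = 0.872.

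| k | Reported | All counted |
|---|---|---|
| 0 | 27/27 = 100% (87.2 to 100) | the same |
| 1 | 27/27 = 100% (87.2 to 100) | 27/28 = 96.4% (81.7 to 99.9) |
| 2 | 27/27 = 100% (87.2 to 100) | 27/29 = 93.1% (77.2 to 99.2) |
| 3 | 27/27 = 100% (87.2 to 100) | 27/30 = 90.0% (73.5 to 97.9) |
| 4 | 27/27 = 100% (87.2 to 100) | 27/31 = 87.1% (70.2 to 96.4) |

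In a tumor stratum of 6, one dropped subject separates 6/6 = 100% (54.1 to 100) from 6/7 = 85.7% (42.1 to 99.6).

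**Step 4. Nodes per subject.** A dropped subject contributes zero nodes. With T nodes in total, the mean is T/27 instead of T/(27 + k), too high by a factor of (27 + k)/27: 28/27 = 1.037 for k = 1 and 29/27 = 1.074 for k = 2.

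**Step 5. Could a failure arise?** Section 1.2.2 gives a per-patient rate of 96.2% in an earlier Phase 2 trial. Used here as an assumption, it implies 27 × 0.038 = 1.03 expected failures, and P(at least one) = 1 − 0.962^27 = 0.65. For assumed rates of 90% and 98% that probability is 0.94 and 0.42. These are chances of any non-localized subject. Only some of those would leave ITT, so the chance of an actual loss is lower.

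**Step 6. What does not move.** Nodal concordance, reverse concordance, pathology agreement, false negative rate and sensitivity (Sections 9.9.5 and 9.9.6) count nodes. A subject with no node taken adds nothing to numerator or denominator. Per-subject concordance and its reverse count only subjects with at least one node identified. Both hypothesis tests in Section 9.9.6 concern nodal concordance.

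**The case against.** The strongest reply is that ITT asks for complete mapping, not for a node found or biopsied. Step 9 of Section 8.4.2 treats probing as complete once every selected count is negative, which also describes a search that finds nothing hot. Sections 8.4.1 and 8.4.2 treat a count below threshold as a negative finding, that is, as a result. The *at least one* wording in Section 9.9.5 presupposes ITT members with none. On this reading a fully probed subject with no hot node stays in as a failure. I accept that as the most natural reading. It is nowhere stated, however, and it does not cover mapping abandoned before the search is finished.

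A reader might infer that Section 4.4 itself drops failures from the analysis. It does not: it governs recruitment, and Section 9.9.1 does not mention replacement. Its effect is to refill the count. It may also be read as meaning a procedure never undertaken, not one with a null result.

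The exposed group is small. A node taken by sight or touch is a biopsy, and any blue node goes to pathology, so those subjects do not meet the replacement condition. The localization rate has no test or success threshold, and the primary objective is safety. These points limit the importance of the concern but do not remove it.

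**Conclusion.** The concern holds in limited form. ITT membership rests on an undefined post-injection condition, and on the literal text a subject whose mapping is abandoned for lack of signal leaves the localization denominator. Any bias is upward. It affects mainly the localization rate and nodes per subject: Lymphoseek in ITT and PP, and the Lymphazurin versions in BITT.

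Each dropped failure is worth about 3 to 4 percentage points at this sample size. One or two would lower the true lower confidence limit from the reported 87.2% to 81.7% or 77.2%. These figures assume the number dropped, assume that all other subjects localize, and use an interval method that the plan does not name for this variable.

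Two stronger readings are tempting. One is that every subject without a hot node is excluded; the protocol's own use of *complete* for probing points the other way. The other is that every BITT and PP result is biased; the concordance, agreement, false negative and sensitivity results are not, because their denominators are nodes or subjects with an identified node. The formal tests and the primary safety endpoint are also unaffected. The change should be made before analysis.

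**What to change.** - **Section 9.9.1 and synopsis:** define ITT by intraoperative mapping started, whatever its result, instead of complete mapping. Reconcile the two base populations (eligible in 9.9.1, all enrolled in the synopsis).
- **Section 9.9.5:** state that a subject with no hot node, or whose mapping was abandoned for lack of signal, counts as non-localized.
- **Section 4.4:** state that replacement does not remove a subject from any analysis set whose definition the subject meets. No separate sentence on the safety set is needed, because its definition already keeps every enrolled subject who was injected.
- **Sensitivity analysis:** add a localization rate on all injected subjects. This also covers mapping never started because no drainage was seen.
- **Reporting:** list every replaced subject with the reason.

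The cost is a few sentences, one extra rate and one listing. No surgical procedure changes. The localization rate may come out slightly less favourable.

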4.5 Subject Identification

After the subject and/or parent or guardian provides written informed consent/assent, the site will assign the subject a 7-digit subject number. Subject numbers are to be assigned in a sequential manner using the following format:

Digits 1 to 2: Trial number "18" Digits 3 to 4: Site number (e.g., "03") Digits 5 to 7: Sequential subject number (e.g., "001", "002", "003", etc.)

For example, the first subject consented at Site 03 is subject number "18-03-001".

Subjects will maintain the same number given at screening for the entire study. If a subject is a screen failure, the number will not be used for any other subject.

5 INVESTIGATIONAL PRODUCT

5.1 Identification of Investigational Product

Lymphoseek[®] (also known as technetium Tc 99m tilmanocept) is a radiopharmaceutical that accumulates in lymphatic tissue by binding to mannose binding receptors (CD206) that reside on the surfaces of dendritic cells and macrophages.

5.2 Investigational Product Dosage and Administration

Subjects will receive an injection of 50 μ g tilmanocept radiolabeled with 0.5 mCi ^{99m}Tc. Lymphoseek may be administered to a subject as a single injection or as multiple injections. The recommended total injection volume for each subject is 0.1 or 0.5 mL administered in a single syringe; 0.5 or 1.0 mL in two syringes (0.25 mL or 0.5 mL each); or 0.4 or 1.0 mL administered in four syringes (0.1 mL or 0.25 mL each). For subjects with melanoma, Lymphoseek will be administered as 1, 2 or 4 intradermal, peritumoral injections or around the excision biopsy site. For subjects with rhabdomyosarcoma or other solid tumors, Lymphoseek will be administered as intradermal peritumoral injection(s) if anatomically appropriate or, if not possible, injection should be performed as determined clinically appropriate by the surgeon.

All doses will be provided in 1 mL BD Luer-LokTM syringes. Each syringe will be delivered with a $\frac{1}{2}$ inch 25-30 gauge needle that can remain or can be replaced with an alternate needle as selected by the surgeon or nuclear medician physician as most appropriate for the individual subject's tumor type. The final administered dose will be \pm 20 % of the intended dose (0.4 to 0.6 mCi).

5.3 Vital Blue Dye

Any investigational site with current experience and standard practice with VBD will use Lymphazurin (1% isosulfan blue injection). Other dyes should not be used. Lymphazurin is commercially available and will be ordered and administered to subjects at the start of or during the surgical procedure as part of their standard of care, per institutional practice. The injection will be performed as deemed appropriate by the surgeon and in accordance with the standard of care at the clinical site.

5.4 Treatment Assignment

In this open-label, non-randomized study, all subjects will receive the same Lymphoseek treatment. The use of Lymphazurin is optional, consistent with institutional practice.

5.5 Packaging and Labeling

Tilmanocept Powder kits ready for radiolabeling will be shipped and stored at the regionspecific Cardinal Health radiopharmacy or clinical site radiopharmacy performing the radiolabeling. Tilmanocept Powder is provided in a 250-microgram vial. A carton contains five vials of tilmanocept. One kit, which is one tilmanocept vial, should be used for each subject. The carton also contains five shield labels and 25 syringe labels. This package has been designed specifically for tilmanocept and protects the vials during shipment, handling, and storage. Cardinal will provide a radiolabeling protocol and Quality Control worksheets. If the clinical site uses a Cardinal Health radiopharmacy, the Cardinal Health radiopharmacy will radiolabel tilmanocept with 0.5 mCi of ^{99m}Tc and deliver single or multiple syringes that are ready for injection to the clinical site radiopharmacy.

5.6 Drug Logistics and Accountability

The investigator (or designated personnel) will confirm receipt of the investigational product in writing and will use the investigational product only within the framework of this clinical study and in accordance with this study protocol. For each subject he/she will keep a record of the investigational product dispensed and store all other forms that accompanied the delivery of the radiolabeled investigational product to the clinical site. These documents are to be filed in the Investigator Site File. Overall drug accountability and reconciliation will be completed by the sponsor or its representative. A list of investigational product vials or syringes and other materials that were returned, or destroyed, must be prepared and signed by the principal investigator or an appropriately qualified designee as documented in the study site responsibility sheet. An overall accountability and reconciliation form of the investigational product will also be prepared and completed. If there are any discrepancies, an explanation for these must be provided.

6 THERAPIES OTHER THAN INVESTIGATIONAL PRODUCT

6.1 **Prior and Concomitant Therapy**

All medications taken 30 days prior to Lymphoseek injection through the Day 4 to 14 followup will be documented.

6.2 Post-Study Therapy

Not applicable.

7 SCHEDULE OF EVALUATIONS AND VISIT DESCRIPTION

7.1 Schedule of Evaluations

Evaluations will be performed during a period of up to 14 days post Lymphoseek administration, following a screening period of maximum 30 days. A schedule of evaluations is provided in the Schedule of Events (see Appendix 1).

7.2 Visit Description

7.2.1 Screening Visit (Day -29 to Day 0)

- Preliminary review of inclusion and exclusion criteria
- Obtain signed informed consent for study participation
- Allocation of unique subject number; this number will be used to document the subject data in the eCRF (case report form) and enrollment log
- Demography Date of birth, gender, and race
- Medical history Medical history will be obtained on all study subjects. All relevant prior medical conditions will be recorded in the eCRFs. Documented medical conditions will also note the month/year of onset and if the condition is active.
- Cancer staging tumor, lymph node, metastasis staging (TNM) (Edge, 2010) information will be collected.
- Performance status will be collected using the Lansky (Lansky et al, 1987) or Karnofsky (Karnofsky et al, 1948) scale as determined by age.
- Vital signs Vital signs will include body temperature (°F or °C), respiratory rate, pulse rate, and systolic and diastolic blood pressures. Prior to obtaining blood pressures and pulse, the subject should be in a resting position for at least 1 minute. Body weight (in pounds) and height (in inches) without shoes will be recorded only at the screening evaluation.
- ECG The ECG (electrocardiogram) reading will be assessed for clinical significance by the investigator, and any clinically significant abnormal findings will be noted on the subject's medical history and should be transmitted to the Central ECG Reader within 1 business day.
- Physical exam Physical examinations will include examination of general appearance, skin, eyes, ears, nose, throat, head and neck (including thyroid), lungs, heart, abdomen, lymph nodes, musculoskeletal, and nervous system. Physical exams that are conducted as standard of care prior to signing informed consent may be used if they are performed within 30 days of injection.
- Clinical laboratory tests Study subjects will have blood and urine samples obtained for hematology, chemistry, and urinalysis (See Section 8.8.2). [Alternatively, blood and urine may be collected on Day 1 if performed before Lymphoseek injection.]
- Concomitant medications (within 30 days before surgery).
- Final check of inclusion/exclusion criteria

7.2.2 Before Enrollment

Within 48 hours prior to receiving the Lymphoseek injection, a urine or serum pregnancy test will be conducted for female subjects of childbearing potential as defined as having reached menarche.

Subject care provider/guardian will be questioned to determine if a change in medical history or concomitant medications has occurred since the last visit.

7.2.3 Preparation of Lymphoseek

The indicated dose of Lymphoseek should be ordered from the Cardinal Health radiopharmacy or clinical site radiopharmacy by the Nuclear Medicine Department once the subject has been scheduled for surgery.

The following medications are not permitted as co-injected drugs: local anesthetics, e.g., procaine, xylocaine, lidocaine, or carbocaine.

7.2.4 Day 1: Before Injection

Before receiving the Lymphoseek injection, vital signs will be collected. Vital signs will include body temperature (°F or °C), respiratory rate, radial pulse rate, and systolic and diastolic blood pressures. Prior to obtaining blood pressures and pulse, the subject should be resting quietly for 1 minute. Body weight and height measurements are not required.

Each syringe will be assayed individually and recorded in the source documentation prior to injection.

7.2.5 Day 1: Injection of Lymphoseek

Injection of Lymphoseek will be at study time 0:00. Subjects will receive 50 μ g tilmanocept radiolabeled with 0.5 mCi ^{99m}Tc by injection as described in Section 5.2.

7.2.6 Day 1: Post Injection

Vital signs will be collected at 10 minutes, 30 minutes, and 1 hour post-injection and after surgery. Vital signs will include body temperature (°F or °C), respiratory rate, pulse rate, and systolic and diastolic blood pressures. Before blood pressures and pulse are obtained, the subject should be resting quietly for 1 minute. Body weight and height measurements are not required. Allowable windows for vital sign collection are as follows:

 $0:10, 0:30 = \pm 3$ minutes 1:00 hour $= \pm 5$ minutes An ECG will be recorded on Day 1 at least 10 minutes after Lymphoseek injection. The ECG reading will be reviewed by the investigator, and any clinically significant abnormal findings will be noted as an AE.

Each syringe will be assayed individually and recorded in the source documentation after injection.

